3.3 Criteria for Premature Termination of the Study: Stopping Rules

Study enrollment will be suspended pending expedited review of all pertinent data by the NIAID DSMB if the following occurs:

• Any death related to Baked Egg or Egg OIT dosing.
- More than 1 severe anaphylactic reaction (see Appendix 3) related to Baked Egg or Egg OIT dosing at any stage of the protocol.
- More than 3 treatment-related non-anaphylaxis severe adverse events (including EoE).
- More than 1 serious suspected adverse reaction occurs (serious and related).
- More than 3 subjects who require more than 1 injection of epinephrine for a single study product related allergic reaction during the study therapy.

4. Selection and Withdrawal of Subjects

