6.1 Enrollment and Randomization

Subjects will be recruited over an 18 month period. Subjects will have an initial baked egg challenge. Approximately the first 40 subjects reacting on the initial baked egg challenge will directly start on Egg OIT. Those who pass the baked egg challenge will be given an initial egg OFC. Those unable to successfully consume ≤ 1444 mg of egg white protein will be randomized in a 1:1 Baked Egg to Egg OIT ratio. Those able to successfully consume more than 1444 mg of egg white protein will not be eligible for the study and will be treated according to local standard of care. Randomization will be done via the project data system; the data system will send an email notification to the site pharmacist and the clinical coordinating center. If accrual capacity is adequate, each of the 5 sites will enter 26 subjects. Entry slots will be reassigned if accrual completion would be delayed because of slow accrual at a given site. Because of the requirement for the baked egg OFC and egg OFC, the screening and baseline visits will be conducted in more than 1 day.

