Treatment of individual reactions should be with either an antihistamine and/or epinephrine, along with IV fluids, albuterol, and steroids as indicated. Generally, for mild and moderate symptoms, the subject should receive antihistamines, and for more severe symptoms, the subjects should receive epinephrine, antihistamines, and then the other medications as indicated. If severe anaphylaxis to egg resulting in hypotension, neurological compromise or mechanical ventilation occurs at any time secondary to baked egg, the subject will be prematurely terminated from dosing.

Antihistamines

If a subject receives antihistamines only, the dosing can be continued.

Epinephrine

If epinephrine is used at home for a baked egg dose, the subject will be brought into clinic for an observed dose with the baked egg product prepared in-clinic. Any individual reaction that requires 2 or more doses of epinephrine (in clinic or at home) counts towards the stopping rules for the protocol.

Egg OIT:

Initial Dose Escalation - the initial day will be done at the Clinical Research Center (or equivalent monitored clinic setting) and consist of Egg OIT dosing, beginning at 0.1 mg egg white solid with graduated doses every 30 minutes up to 25 mg (if tolerated) on Day 1. The Egg OIT assignment group (that failed the baked egg challenge) will only escalate to 12 mg egg white solid maximum on Day 1. Subjects will not have active wheezing or a current flare of atopic dermatitis. If symptoms occur preventing escalation to 25 mg (12 mg in the Egg OIT assigned group), the highest tolerated dose (at least 3 mg) will be accepted as the "desensitization" dose for further escalation (See Exhibit 1, Section 6). The maximum tolerated dose on Day 1 (e.g., 3 mg, 6 mg, 12 mg, or 25 mg egg white solid) will be given on Day 2 as a single dose under observation at the Clinical Research Center. If moderate symptoms occur on Day 2, the subject will return to the Clinical Research Center on Day 3 for the next lower dose (must be at least 3 mg) under direct observation. If moderate symptoms re-occur, consultation with the Study Chair or Co-Chair is warranted to determine the next course of action. If symptoms prevent initial escalation desensitization dosing to 3 mg, the subject will be dropped from active treatment due to desensitization failure and followed longitudinally. Subjects tolerating 3 mg, 6 mg, or 12 mg egg white solid will go home to remain on that dose daily and

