If a subject fails dose escalation after three consecutive (with 2-4 weeks between) attempts, he/she will be considered a dose escalation failure and the last tolerated dose will be accepted as the maintenance dose. For a completed dose escalation with no symptoms, subjects should be observed for 30 minutes. For mild symptoms, subjects should have a 1-2 hours post-protocol observation period. For moderate to severe symptoms, the observation period should be at least 4 hours and up to 24 hours based on symptoms and treatment regimen needed to stabilize the subject.

Any subject deemed to have severe symptoms including hypoxia, hypotension or change in mental status (stage 3 defined in Appendix 3) and receives aggressive therapy at any time should be discussed with the Study Chair or Co-Chair and discontinued from active therapy.

For specific questions related to dosing escalation or continuation of the same dose that are not answered in the above protocol, the Study Chair or Co-Chair will be available for questions and decision-making.

Any subject who discontinues build-up dosing due to repeated allergic reactions to the egg product will have his/her mechanistic blood drawn within approximately 1 week of discontinuation of therapy.

6.4.2 Treatment for reactions during the Build-Up and Maintenance Phases

Treatment of individual reactions should be with either an antihistamine and/or epinephrine, along with IV fluids, albuterol, and steroids as indicated. Generally, for mild and moderate symptoms, the subject should receive antihistamines, and for more severe symptoms, the subjects should receive epinephrine, antihistamines, and then the other medications as indicated. If severe anaphylaxis (stage 3 defined in Appendix 3) occurs at any time, dose escalation will stop and the dose will be reduced to the last tolerated dose (must be at least 350 mg egg white solid) and the subject continued on that dose as long-term maintenance without further escalation.

Antihistamines

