If a subject receives antihistamines only, the dose escalation can be continued. If symptoms during a build up day require antihistamines in multiple doses or in combination with other medications (except epinephrine), there should be a dose reduction by 1-2 doses with the next dose given in the CRC. If dose escalation fails or requires treatment after 2 more escalation attempts each spaced 2 to 4 weeks apart, the dose should be reduced to the last tolerated dose (must be at least 350 mg egg white solid to continue) and continued long term without further escalation.

Epinephrine

Any reaction (in clinic or at home) that requires 2 or more doses of epinephrine counts towards the stopping rules for the protocol. Further dose escalation would not occur in this individual and maintenance on the last tolerated dose (must be greater than 350 mg) would be maintained.

Clinic

If a single administration of epinephrine is required during in clinic escalation, the dose should be reduced by 2 doses, and the subject continued on that dose for 4 weeks. After 4 weeks at the reduced dose, an escalation attempt may be tried in clinic.

If a single administration of epinephrine is required a second consecutive time during this escalation attempt, the dose should be reduced by 2 doses, and the subject continues on that dose for 6-8 weeks. After 6-8 weeks at the reduced dose, an escalation attempt may be tried in clinic.

If a single administration of epinephrine is required a third consecutive time during this escalation attempt, the dose should be reduced by 2 doses (if the reduced dose is at least 350 mg egg white solid) and the subject continued on that dose as long-term maintenance without further escalation.

Home

If a single administration of epinephrine use occurs during dosing at home, this epinephrine use is not counted as one of the uses described above, unless severe anaphylaxis occurs at home. The subject should return to clinic for an observed dose prior to resuming any dosing at home. The investigator may or may not decide to dose reduce depending on the specific circumstances surrounding the reaction.

MAINTENANCE PHASE (PRE 1 YEAR 7444 MG EGG WHITE PROTEIN OFC PHASE)

This phase consists of the subject receiving the maximum achieved daily dose of either baked egg or egg white solid OIT (as described above) for at least 8 weeks at home. The subject will continue to follow an egg-restricted diet for the duration of the study.

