4.2 Discussion of Study Design, Including the Choice of Control Groups

The design considers important safety issues:

- All dose escalations will be supervised in the clinic.
- The Egg OIT assignment group (that failed the baked egg challenge) will only escalate to 12 mg egg white solid maximum during the initial escalation on Day 1.
- OFC can delineate individuals who can ingest egg safely in a supervised setting.
- The relationship of egg-specific IgE to OFC results is unknown in individuals consuming baked egg or 350 2500 mg of egg white solid daily for up to a year. Thus, after long-term therapy, an egg OFC will be needed to determine sustained unresponsiveness irrespective of their egg-specific IgE level, and this will be performed safely in a supervised setting.

In addition, study enrollment will be suspended pending expedited review of all pertinent data by the NIAID DSMB if the following occurs:

- Any death related to Baked Egg or Egg OIT dosing.
- More than 1 severe anaphylactic reaction (see Appendix 3 of the protocol) related to Baked Egg or Egg OIT dosing at any stage of the protocol.
- More than 3 treatment-related non-anaphylaxis severe adverse events (including EoE).
- More than 1 serious suspected adverse reaction occurs (serious and related).
- More than 3 subjects who require more than 1 injection of epinephrine for a single study product related allergic reaction during the study therapy.

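### The five safety triggers suspend enrolment only: none calls for a DSMB decision on dosing in children already enrolled, and after accrual closes the stated action has nothing to act on

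*Protocol*

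**What the plan says.** Protocol 3.3 attaches a single consequence to its list of triggers: "Study enrollment will be suspended pending expedited review of all pertinent data by the NIAID DSMB". SAP 4.2 has the same: "study enrollment will be suspended pending expedited review of all pertinent data by the NIAID DSMB". The synopsis lists the triggers with no consequence at all.

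In the order of 3.3, the triggers are:

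1. any death related to dosing;
2. more than one severe anaphylactic reaction "related to Baked Egg or Egg OIT dosing at any stage of the protocol";
3. more than three treatment-related severe events other than anaphylaxis;
4. more than one serious suspected adverse reaction;
5. more than three children who each need more than one epinephrine injection for a single product-related reaction.

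The dosing sections confirm that home and clinic reactions both count. For Baked Egg (6.4.1): "Any individual reaction that requires 2 or more doses of epinephrine (in clinic or at home) counts towards the stopping rules for the protocol". For Egg OIT (6.4.2): "Any reaction (in clinic or at home) that requires 2 or more doses of epinephrine counts towards the stopping rules for the protocol".

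On timing, 6.1 says "Subjects will be recruited over an 18 month period", and each child is treated for two years.

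**The concern.** The triggers measure harm from dosing, so the children exposed to whatever hazard they detect are mainly those already dosing. The stated action reaches only children not yet enrolled. That is so even while accrual is open, and after accrual closes there is no enrolment to suspend. The text words expedited review only as what that suspension waits for, so it does not expressly say that review is required then.

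Suppose a fourth child needs a second epinephrine injection for one reaction during second-year dose increases. Trigger 5 is met, and that child's escalation stops. The text does not say that the DSMB must decide whether dose increases go on in the other children. If the event was not classed as serious, the only stated route to the DSMB is its next regular report.

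No endpoint or analysis is at stake. The issue is whether a pre-specified safety rule says what happens to the children it is meant to protect.

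**Working it through.** **Step 1: what each layer of protection does**

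| Provision | Acts on | Tied to a trigger? |
|---|---|---|
| 3.3 and SAP 4.2: suspend enrolment, expedited DSMB review | children not yet enrolled | yes |
| 7: DSMB may recommend withdrawals or terminating the study | any child, or the study | no |
| 7.4.2: sponsor, FDA and DSMB may suspend treatment study-wide | all children | no |
| 6.4.2: after repeat epinephrine in Egg OIT, "Further dose escalation would not occur in this individual" | affected child | individual rule |
| 6.4.2: after severe anaphylaxis in Egg OIT, "dose escalation will stop and the dose will be reduced to the last tolerated dose" | affected child | individual rule |
| 4.3.1 and the end of the build-up algorithm in 6.4: stop therapy after severe symptoms treated aggressively | affected child | individual rule |
| 6.4.1: Baked Egg dosing ends after severe anaphylaxis | affected child | individual rule |

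No row both depends on a trigger and reaches the other enrolled children.

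**Step 2: how events reach the DSMB**

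Under 7.5.3 serious adverse events go to the DSMB on an ongoing basis. Triggers 1 and 4 are serious by definition, and severe anaphylaxis (trigger 2) would usually qualify. Triggers 3 and 5 do not require seriousness. Under 7.2 a systemic dosing reaction goes on a Study Product Administration form and reaches the AE/SAE form only if serious. Under 9.6 the DSMB's regular reports cover dose escalation success and dose-limiting events. The gap therefore lies mainly in non-serious events under triggers 3 and 5.

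**Step 3: how much dosing time falls after accrual closes**

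The plan states no figure, so there is none to reproduce. Inputs: accrual A = 18 months (6.1) and dosing T = 24 months (2.1). The entry pattern is not given. I assume uniform entry and vary it.

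For T ≥ A, share after close = 1 − (A − mean entry month)/T.

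- Uniform, A = 18: 1 − (18 − 9)/24 = 62.5%.
- Uniform, A = 12: 1 − (12 − 6)/24 = 75%. Uniform, A = 24: 1 − (24 − 12)/24 = 50%.
- A = 18, linearly front-loaded (mean entry month 6): 1 − 12/24 = 50%. Back-loaded (mean entry month 12): 1 − 6/24 = 75%.
- A = 18, uniform, 15% withdrawal by month 24 at a constant rate (6/40 in the prior egg OIT trial, protocol 1.1): mean dosing time is 22.15 months, of which 8.64 fall before close, so 1 − 8.64/22.15 = 61.0%.

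**Step 4: first-year build-up**

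For a phase that starts at entry and lasts d ≤ A, share after close = d/(2A). Months = weeks × 12/52.18.

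- 32 weeks (synopsis) = 7.36 months: 7.36/36 = 20.4%.
- 44-week maximum (section 3) = 10.12 months: 10.12/36 = 28.1%.

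So 72–80% of build-up time falls while accrual is still open.

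**Step 5: second-year re-escalation**

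The longest case is a child who starts at the 350 mg minimum, with nine steps to 2500 mg. That takes 18 weeks (4.14 months) at 2 weeks a step, or 36 weeks (8.28 months) at 4 weeks a step, starting at month 12.

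- 18 weeks: mean time before close = (4.14²/2 + 4.14 × 1.86)/18 = 0.90 months, so 78% falls after.
- 36 weeks: (6²/2)/18 = 1.00 month, so 88% falls after.
- With 24-month accrual these become 59% and 67%.

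The documents do not say how many children will re-escalate.

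**The case against.** The case against has five parts.

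- **The rule plainly continues after accrual.** Section 3.3 is headed as criteria for ending the study, trigger 2 covers every stage, and 6.4.2 counts repeat-epinephrine reactions during maintenance. That counting would be pointless unless the rule still operated. A reader might infer that expedited review lapses when accrual closes. The documents do not support that: review would probably still happen. What stands is that the text does not expressly require it.
- **Authority over dosing exists.** A reader might infer that dosing could not be stopped. Sections 7 and 7.4.2 say otherwise. What stands is that these powers are discretionary and linked to no trigger.
- **Individual protections are substantial.** Besides stopping escalation, 4.3.1 and 6.4 call for discontinuing children with severe symptoms who are treated aggressively. This is correct, but it covers only the affected child, whereas a count across children is there to detect a signal for the rest.
- **Repeat epinephrine may be classed as serious** under the important-medical-event criterion in 7.2.2, and so reach the DSMB promptly. This narrows the gap but depends on judgement case by case.
- **The lack of an automatic dosing pause is defensible.** Section 6.4 says that missed Egg OIT doses carry risk, and more than seven consecutive missed days ends therapy. I accept this. The point is the absence of a required decision, not of a pause.

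**Conclusion.** The point holds as a cheap improvement to a safety rule. All five triggers lead to one automatic study-level action, which does not reach children already dosing and has nothing to suspend after accrual. No safety authority is missing, and no endpoint or analysis changes. The practical gap is mainly non-serious events under triggers 3 and 5.

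The 62% figure (range 50–75%) is context only. It assumes uniform entry and full two-year dosing, and it pools steady maintenance with the Baked Egg arm, where 6.4 describes reactions as rare. A reader might take it as the share of risk left uncovered. The documents give no event rates by phase, so they do not support that. First-year build-up, which Egg OIT children enter at the start, falls mostly inside the accrual period. The 78–88% for re-escalation applies to a child starting from the minimum dose.

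The situation is not hypothetical for the SAP: section 2.1 describes randomisation in the past tense with the Year 2 challenge still ahead, while 4.2 repeats the enrolment-only action.

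**What to change.** Reword the lead sentence of protocol 3.3 and mirror it in SAP 4.2, for example:

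> If any of the following occurs while any subject is receiving study therapy, expedited DSMB review is required whether or not accrual is open. Any remaining enrolment is suspended until that review is complete, and the DSMB records whether initial escalations, dose increases and ongoing dosing continue, under the authority in Section 7.4.2.

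Do not add an automatic hold on daily maintenance dosing, because of the missed-dose risk described in 6.4.

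The cost is a protocol amendment. Under 11.1 it needs approval by DAIT/NIAID/NIH, the DSMB and the EC/IRB, and submission to FDA. It can be bundled with another amendment. The SAP edit is for consistency only. The downside is a possible ad hoc DSMB review after accrual closes. If the sponsor already intends to work this way, the edit only writes it down.

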4.1 Inclusion Criteria

Subjects who meet all of the following criteria are eligible for enrollment as study subjects:

- Age 3 through 16 years with a serum IgE [UniCAPTM] to egg of \geq 5 kU_A/L [determined by UniCAPTM within the past 12 months].
- Reacting to the baked egg challenge OFC with dose limiting symptoms (approximately 40 subjects), OR
- Reacting on an initial egg OFC with dose limiting symptoms to a cumulative dose of 1444 mg egg white protein or less after passing the initial baked egg OFC.
- Written informed consent from subject and/or parent/guardian.
- Written assent from all subjects as is appropriate.
- All females of child-bearing age must be using appropriate birth control.

4.2 Exclusion Criteria

Subjects who meet *any* of these criteria are not eligible for enrollment as study subjects:

- History of anaphylaxis to egg resulting in hypotension, neurological compromise or mechanical ventilation.
- Chronic disease (other than asthma, atopic dermatitis, rhinitis) requiring therapy (e.g., heart disease, diabetes).
- Active eosinophilic gastrointestinal disease in the past 2 years.
- Participation in any interventional study for the treatment of food allergy in the past 6 months.
- Subject is on "build-up phase" of immunotherapy (i.e., has not reached maintenance dosing). Subjects tolerating maintenance allergen immunotherapy can be enrolled.
- Severe asthma (2007 NHLBI Criteria Steps 5 or 6, see Appendix 2).
- Mild or moderate (2007 NHLBI Criteria Steps 1-4) asthma with any of the following criteria met:
 - FEV1 <80% of predicted, or FEV1/FVC <75%, with or without controller medications (only for age 6 or greater and able to do spirometry), or
 - ICS dosing of >500 mcg daily fluticasone (or equivalent inhaled corticosteroids based on NHLBI dosing chart), or
 - 1 hospitalization in the past year for asthma, or
 - 1 ER visit in the past 6 months for asthma.
- Use of steroid medications (IV, IM or oral) for asthma in the following manners:
 - history of daily oral steroid dosing for >1 month during the past year, or
 - o burst or steroid course in the past 3 months, or
 - \circ >2 burst oral steroid course in the past year.

- A burst of IV, IM or oral steroids of more than 2 days for an indication other than asthma in the past 30 days.
- Inability to discontinue antihistamines for the initial day of escalation, skin testing or OFC.
- Use of omalizumab or other non-traditional forms of allergen immunotherapy (e.g., oral or sublingual) or immunomodulator therapy (not including corticosteroids) or biologic therapy (e.g., infliximab, rituximab, etc.) within the past year.
- Use of β-blockers (oral), angiotensin-converting enzyme (ACE) inhibitors, angiotensinreceptor blockers (ARB) or calcium channel blockers.
- Use of investigational drug within 90 days or plan to use investigational drug during the study period.
- Pregnancy or lactation.

4.3 Premature Subject Termination from the Study

4.3.1 Criteria

No subject initiating therapy in this trial will be replaced.

Any subject may be prematurely terminated from additional allergen exposures, but maintained on longitudinal follow-up for the following reasons:

• Anaphylaxis resulting in hypotension, neurological compromise or mechanical ventilation secondary to Baked Egg or Egg OIT dosing or any egg food challenge.

Any subject deemed to have severe symptoms and receives aggressive therapy at any time should be discontinued from further therapy, including the following:

- Poor control or persistent activation of secondary atopic disease (e.g., AD, asthma).
- Started on ARBs, ACE inhibitors, beta-blockers, or other prohibited meds and there are no alternative meds available per the prescribing doctor, they will be removed from further treatment.
- Pregnancy.
- Egg OIT Group subjects:
 - Circumstances (e.g., concurrent illness, such as gastroenteritis) requiring missed Egg OIT maintenance dosing of >7 consecutive days (this does not include subjects intentionally removed from therapy to administer an OFC off therapy).
 - Non-adherence with home Egg OIT dosing protocol (excessive missed days; i.e., >3 consecutive days missed on 3 occasions), would be a safety issue warranting discontinuation.

Any subject may be prematurely terminated from the study if:

- The subject elects to withdraw consent from all future study activities, including followup.
- The subject is "lost to follow-up" (i.e., no further follow-up is possible because attempts to reestablish contact with the subject have failed).
- The subject has biopsy documented Eosinophilic Esophagitis (EoE).

• The subject dies.

